### 6.3 Baseline and Post-Randomization Measures

Measurements to evaluate safety, adherence, and outcomes are summarized in Table 2. The outcomes, derived from hyperglycemic clamp procedures, will be measured at baseline, 12 months (end of treatment), and 15 months post randomization (end of washout). OGTT outcomes measurements and blood sampling for other outcomes will be performed at baseline, 6 and 12 months following randomization (on treatment) and then at 15 and 21 months (off treatment). Hyperglycemic clamp and OGTT outcomes measures are described in detail above. Other measurements are discussed below.

Table 2: Timeline of Outcomes, Safety Testing, and Adherence Measures

	Baseline/ Pre random- ization	Post Randomization Month						
		3	6	9	12	15	18	21
Physical								
Height	x							

**CONFIDENTIAL**

	Baseline/ Pre random- ization	Post Randomization Month						
		3	6	9	12	15	18	21
Weight	x	x	x	x	x	x	x	x
Waist / Hip circumference	x				x	x		x
Blood pressure	x	x	x	x	x	x	x	x
Outcomes								
Hyperglycemic clamp & AIR max	x				x	x		
OGTT	x		x		x	x		x
HbA1C	x	x	x	x	x	x	x	x
Questionnaires	x							
Sleep (Pittsburgh Sleep Questionnaire, Epworth Sleepiness Scale, Berlin Questionnaire)	x							
Biomarkers	x		x		x	x		x
Stored Specimens								
DNA	x							
Plasma / Serum	x		x		x	x		x
Urine	x		x		x	x		x
Safety								
SMBG for those on insulin	x	x						
Hemoglobin or Hematocrit	x		x		x			
Blood chemistries**	x		x					
Adverse events	x	x	x	x	x	x	x	x
Pregnancy test + (local measure)	x	x	x	x	x	x	x	x
Medication adherence	x	x	x	x	x			

\*\* fasting serum ALT and creatinine; pregnancy tests as needed based on symptoms and menstrual history

### 6.3.1 Physical Measures

Height will be measured with a stadiometer. Weight will be measured with a calibrated electronic scale. Waist and hip circumferences will be measured at the mid-point between the iliac crest and the lowest rib (waist), and at the top of the femur (hip) with the participant standing upright.

### **6.3.2 Sleep Assessments**

During screening, participants will complete the Pittsburgh Sleep Questionnaire, Epworth Sleepiness Scale and Berlin Questionnaire for analysis of self-reported sleep-related measures as potential predictors of response to treatment.

### **6.3.3 Safety Measures**

Acute treatment effects will be assessed using home glucose monitoring for those assigned to insulin therapy, plus scheduled clinic visits and telephone contact. The study will provide blood glucose monitors and strips to participants assigned to the insulin arm for use for the first 3 months of the intervention (baseline to 3 months). During the insulin treatment phase, participants will record fasting blood glucose once daily, in the morning, to guide dose adjustment for the insulin. Routine chemistries consisting of hemoglobin or hematocrit (local lab), serum liver enzymes (ALT) and creatinine will be collected for evaluation of liver and kidney function at screening and at six months during treatment. Adverse events (AE) will be surveyed at each visit using a standardized questionnaire. Pregnancy tests (local lab) will be performed in women with child-bearing potential prior to study procedures at each visit.

### **6.3.4 Participant Protocol Adherence**

Pill counts will be performed at each visit from run-in to the end of the treatment period. Similarly, insulin or liraglutide pen residual volume will be determined. Participants will be asked to bring all medications to all visits. Self-monitoring blood glucose (SMBG) data will be reviewed at the 3 month study visit for subjects assigned to insulin treatment.

## **6.4 Visit Windows**

Participants will be encouraged to complete visits within a 1-2 week window before or after the scheduled study visit. All participants will have a visit calendar generated at the time of randomization to assist in keeping visits scheduled as required.

## **7 SAFETY / HUMAN SUBJECTS PROTECTION**

This trial will be conducted in compliance with the protocol and all applicable regulatory requirements. All participating clinical sites must have a Federal-wide Assurance with the Office for Human Research Protections. All sites will follow HIPAA regulations.

Prior to study initiation, the protocol and the informed consent documents will be reviewed and approved by the IRB at each participating clinical site and by an independent Data and Safety Monitoring Board (DSMB). Any amendments to the protocol or consent materials must be approved by the DSMB and the IRBs before implementation.

**CONFIDENTIAL**

## ***7.1 Data and Safety Monitoring Board (DSMB)***

A DSMB comprised of appropriately qualified and conflict-free independent experts is appointed by the National Institute of Diabetes and Digestive and Kidney Diseases (NIDDK) and provides input to the Institute. Board members are chosen by the NIDDK without consultation with the study investigators. The purpose of the Board is to assure independent review as to whether study participants are exposed to any unreasonable risk because of study participation, and to monitor study progress and integrity. In addition to safety monitoring, the Board can review unblinded study data and make recommendations for early termination of studies for achieving an end point or for futility. Before any of the RISE studies can begin, the DSMB, in addition to the local IRBs, must approve the protocol. Any subsequent major changes to the protocol must also be approved by the DSMB and IRBs.

Following each DSMB meeting, a summary of DSMB recommendations is provided to the IRB of each participating clinical center and other institutional monitoring committees/boards as needed.

## ***7.2 Data and Safety Monitoring Plan***

### **7.2.1 Informed Consent**

The informed consent process will be conducted by qualified study personnel. All participants must read, sign and date a consent form prior to participation in any stage of the study. The informed consent will be revised and participants re-consented whenever there is new, clinically significant information regarding the safety of the interventions, when a relevant protocol amendment is approved, or when any new information becomes available that may affect an individual's participation in the study. At any time during the study, participants will have the option to withdraw from participation without repercussion. In the event that a participant withdraws, study medication will no longer be provided but the arm to which the participant was randomized will remain blinded, as the analysis will be one of intention-to-treat.

### **7.2.2 Safety Review Plan and Monitoring**

- A. Justification of Sample Size – See Section 9.3.
- B. Stopping Rules – The DSMB may suggest terminating a study arm at any time for safety or efficacy reasons. Details of interim analysis plans and stopping rules can be found in Sections 9.4 and 9.5.

**CONFIDENTIAL**

- C. Safety Monitoring Committee and Safety Review Officer – The study will appoint an internal Safety Monitoring Committee (SMC) which will review AEs or other safety-related problems sent to them from the field. The RISE SMC will review AEs in a blinded manner. An external Safety Review Officer will evaluate any serious adverse events (SAE) where the SMC is not in agreement about whether the event is related to study drug as well as certain specified SAEs of concern (e.g., pancreatitis). The Safety Review Officer will not be blinded to study intervention.
- D. Safety Review Plan – The DSMB will meet at least twice yearly either in person or by conference call to review study progress and safety as described in Section 7.1.

### **7.2.3 Confidentiality**

- A. Protection of subject privacy – Participants are identified within the study only by their RISE Participant ID. No confidential identifiers are used in any data collection.
- B. Database Protection – All files are stored in a locked cabinet at the clinical centers, and data are entered into a secure, password-protected website maintained by the CoC. The CoC holds no personal identifiers and stores the data on its enterprise server accessible only by approved staff. At the end of the study, all records will be kept in a secure locale for a period dictated by local IRB and Institutional policies as well as federal regulations, whichever is longest.
- C. Confidentiality During AE Reporting – AEs and SAEs are recorded on data collection forms and reported to the CoC without personal identifiers. Identifiers on accompanying documents (such as medical records) are removed before submission to the CoC and any subsequent transfer to the Safety Monitoring Committee and/or Safety Review Officer.

### **7.3 *Expected Side Effects***

The RISE Study will use the following medications: metformin, insulin glargine and liraglutide.

**Metformin:** Known adverse effects associated with metformin are primarily gastrointestinal (diarrhea, nausea, vomiting, abdominal bloating, flatulence, anorexia), hematologic (reduced vitamin B12 levels and, rarely, megaloblastic anemia), and the rare possibility of lactic acidosis. The risk of lactic acidosis associated with metformin use will be minimized by (1) monitoring liver transaminases, (2) monitoring renal function, and (3) temporary discontinuation of metformin before radiologic studies involving the injection of contrast dye, surgical procedures requiring reduced fluid intake, and serious illness that might be associated with hypoxia, dehydration, or shock.

**CONFIDENTIAL**

**Insulin glargine:** The side effects of insulin glargine include hypoglycemia and weight gain. The occurrence of hypoglycemia will lead to insulin dose adjustment at the discretion of the investigator. Participants will be counseled about the possibility of weight gain while on insulin therapy and given dietary counseling and resources. Participants on insulin will perform SMBG to minimize the risk of hypoglycemia.

**Liraglutide:** The most common adverse effects associated with liraglutide are gastrointestinal and include nausea, vomiting, and diarrhea. An increased risk of pancreatitis has also been reported. A history of previous pancreatitis is an exclusion criterion and an absolute contraindication to continuing liraglutide. In addition, increased levels of calcitonin, which are associated with medullary thyroid carcinoma, a rare form of thyroid cancer, have been reported in some animal and human studies. A history of medullary thyroid cancer or a family history of MEN-2 is an exclusion criterion in RISE.

## **7.4 Risk Management**

Glucose management (including study medications) will be provided free of charge to RISE Study participants while participating in the study. Participants will receive training about the proper use of hypoglycemic medications as well as education about the symptoms, causes and response to episodes of hyper- and hypoglycemia. Participants who develop symptomatic hypo- or hyperglycemia, or experience any side effects of medications or study procedures will be instructed to call the clinical site. The following procedures will be implemented to minimize risk to participants:

- *Hyperglycemia:* Participants will be instructed regarding the signs and symptoms of hyperglycemia and are to call the clinic with any concerns. To minimize the risk of symptomatic hyperglycemia, the following procedures will be followed:
  - If HbA1c >7% at any routine quarterly visit, therapy will be invigorated by frequent telephone contact and/or visits to encourage optimal medication adherence and lifestyle choices. HbA1c will be obtained at the next quarterly visit. If HbA1c remains >7% but  $\leq$ 8%, frequent contact will be maintained.
  - If HbA1c >8.0% at any routine quarterly visit, therapy will be invigorated and HbA1c will be repeated after 6 weeks. If it remains >8.0%, outcome assessment will be scheduled in 2 weeks (i.e., regardless of time since randomization).
  - If at any time – either a routine visit or when a participant is brought in due to symptoms – the HbA1c >9%, the HbA1c will be repeated within 2 weeks and, if confirmed, the participant will be scheduled for immediate outcome measurement.

- Metabolic decompensation: In the unlikely event that a study subject develops metabolic decompensation, defined as hyperglycemia (plasma glucose >300 mg/dl) accompanied by significant symptoms (e.g., vomiting, dehydration, lethargy) and/or moderate or large urinary ketones, the participant will be evaluated to determine if temporary use of insulin therapy is required. Once insulin is started, the site will attempt to wean insulin within 4 weeks. If insulin cannot be weaned off within 4 weeks, the patient will be censored at that time.
- If outcome measurements are performed prior to the scheduled time points of 12 or 15 months, once completed the participant will be referred back to their primary care provider for further care.
- *Gastrointestinal (GI) symptoms* are a common occurrence with metformin and liraglutide. However, these symptoms more commonly occur early in the course of treatment. All eligible participants will be slowly titrated to the maximal tolerated doses of metformin or liraglutide, in order to minimize gastrointestinal side effects. For metformin, the dose will be started at 500 mg daily and titrated slowly to 1000 mg bid. If GI side effects develop and are mild, the patient will be encouraged to remain on the study medication. If GI side effects are moderate or difficult to tolerate, metformin will be reduced to the next lowest dose (for example, 1000 mg bid to 1000 mg + 500 mg; 1000 mg + 500 mg to 500 mg bid; etc.). If symptoms persist, metformin will be reduced to the next step. If GI symptoms resolve, metformin will be re-escalated by 500 mg per day each week until reaching the previously tolerated dose. The participant will continue on the maximum tolerated dose. A similar procedure will be followed for liraglutide, with the relevant doses being 0.6, 1.2 and 1.8 mg daily.
- *Anemia* may be an adverse effect of metformin. It is defined as a hematocrit <30.0%, a hemoglobin <10 gm/dl, a decline in hematocrit by 4% from study entry, or a decline in hemoglobin by 2 gm/dl from study entry. If anemia persists for more than six months despite appropriate therapy, consideration will be given to discontinuing study medication.
- *Renal insufficiency* increases the risk of lactic acidosis associated with metformin. To assess renal insufficiency, serum creatinine and estimated GFR (eGFR) will be calculated using the CKD-Epi equation (ref . Ann Intern Med. 2009;150(9):604-612.) at screening and after six months on therapy. Participants must have an eGFR of 45 mL/minute/1.73 m^2 or higher to be eligible. Metformin will be discontinued if eGFR is below 30 mL/minute/1.73 m^2 at the Month 6 visit. If eGFR ≥30 and <45 mL/minute/1.73 m^2 then the RISE Safety Committee will review the case to assess the benefits and risks of continuing treatment, and make a

recommendation to the clinical center investigators about whether to continue the participant on metformin.

- *Mild hypoglycemia* is common in subjects with prediabetes or diabetes being treated with medications to lower glucose levels into or near the normal range. Participants will be educated to recognize and treat mild hypoglycemic episodes and to contact study staff to report hypoglycemic episodes or receive advice. Adjustments to study medication will be made when appropriate.
- *Severe hypoglycemia* is defined by the need to be treated with glucagon, the need for a third party to resolve a hypoglycemic episode, or loss of consciousness or seizure. Study medications will be adjusted downward as appropriate.
- *Metformin and its placebo* are temporarily discontinued 24 hours before, during, and for 48 hours after any of the following events to reduce the risk of lactic acidosis: 1) procedure involving the injection of contrast dye; 2) surgery or other procedure requiring general anesthesia; 3) any illness that could be associated with hypoxia, circulatory failure, or dehydration; 4) hospitalization. Serum creatinine will be rechecked no sooner than 48 hours after the conclusion of the event and study medication recommenced if appropriate.
- Other indications for temporary or permanent discontinuation of study medication include:
  - *Pregnancy:* Study medications will be discontinued if a participant becomes pregnant. The participant will be referred to a high risk obstetrics clinic for further care. Study medications will not be administered if a participant plans to become pregnant.
  - *Lactation:* No study medication will be administered to women who are nursing a baby.
  - *Lactic acidosis:* Any study participant who experiences a bout of lactic acidosis will have metformin and metformin placebo permanently discontinued.
  - *Dermatological problems:* Any study participant who experiences severe dermatological problems, such as urticaria, bullous rashes, exfoliative dermatitis, Stevens-Johnson syndrome, thought to be related to study medication will have study medication permanently discontinued.
  - *Pancreatitis:* Any study participant who is diagnosed with pancreatitis during the study will have liraglutide permanently discontinued.
  - *Medullary thyroid carcinoma:* Any study participant who is diagnosed with medullary thyroid carcinoma during the study will have liraglutide permanently discontinued.
- Adverse effects of the study procedures may occur very rarely and include:
  - *Glucose injection and infusion:* Irritation of a vein resulting in phlebitis can occur with administration of concentrated glucose solutions. The risk will be decreased by

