**CONFIDENTIAL**

To minimize non-compliance due to gastrointestinal side effects, participants will be titrated over four weeks from a starting dose of 500 mg once daily to a maximum dose of 1000 mg bid. Participants will remain on the maximum tolerated dose of metformin throughout the study. If participants are unable to tolerate metformin they will continue in the study but will not take the medication.

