#### **3.4.4 Liraglutide plus Metformin**

Liraglutide will be started at a dose of 0.6 mg subcutaneously, once daily. This dose will be continued for one week, after which subjects will increase the daily dose to 1.2 mg if they have tolerated the 0.6 mg daily dose. Likewise, after one week at 1.2 mg daily, the dose will be increased to 1.8 mg daily, the maximal recommended daily dose in the treatment of diabetes. If participants cannot tolerate the higher dose, they will revert back to the previously tolerated dose and will remain on that maximal tolerated daily dose for the duration of the study. Once the maximal dose of liraglutide has been reached and is tolerated, metformin will be initiated and titrated as described above. If the combination of the medications produces intolerable adverse effects, liraglutide treatment will be retained in preference to metformin.

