#### **3.4.5 Insulin Glargine Followed by Metformin**

Insulin will be titrated over a period of one month based on self blood glucose monitoring to achieve a fasting blood glucose of 80-90 mg/dl without hypoglycemia, and then continued with dose adjustment to maintain the fasting glucose in this range. Insulin glargine has been shown to be titratable in individuals with prediabetes and established diabetes to achieve fasting glucose concentrations of <95 mg/dl without a marked increase in recurrent or severe hypoglycemia [44]. Following 3-months of insulin treatment, insulin glargine will be discontinued and metformin will be commenced and titrated as above.

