#### **3.4.7 Medication Wash-out and Post-treatment Follow Up**

Following the completion of the intensive re-assessments (hyperglycemic clamp and OGTT) after 12 months of the intervention, study medications will be stopped and the participants will continue to be followed off medications, for a minimum of 3 months and up to 9 months, depending on the time of randomization within the 5-year study period. At the end of the first 3 months off treatment (i.e., 15 months after randomization), the hyperglycemic clamp and OGTT will be repeated to determine the durability of the effects of the active interventions on  $\beta$ - and

$\alpha$ -cell function. Although it is unlikely in this study population, participants may experience deterioration in  $\beta$ -cell function during this 3-month wash out period, and require rescue therapy. Criteria for rescue, and protocol-specified rescue therapy, are described below (see Section 7.4). Participants who do not require rescue will undergo the final clamp and OGTT procedures at the end of the 3-month washout period. They will then continue to remain off study medications and retesting will occur 9-months following discontinuation of the intervention (i.e., 21 months after randomization). The rescue protocol will be utilized, as needed, during this last 6-month follow-up period. Following the complete 9-month washout period, patients will be referred to their primary care provider for further follow up.

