## **3.6 *Exclusion criteria***

1. Underlying disease likely to limit life span and/or increase risk of intervention or an underlying condition that is likely to limit ability to participate in outcomes assessment
2. An underlying disease that affects glucose metabolism other than type 2 diabetes
3. Taking medications that affect glucose metabolism, or has an underlying condition that is likely to require such medications
4. Active infections
5. Renal disease (eGFR <45 mL/minute/1.73 m)
6. Anemia (hemoglobin <11 g/dl in women, <12 g/dl in men) or known coagulopathy

7. Cardiovascular disease, including uncontrolled hypertension. Participants must be able to safely tolerate administration of intravenous fluids required during clamp studies.
8. History of conditions that may be precipitated or exacerbated by a study drug:
  - a. Pancreatitis
  - b. Serum ALT more than 3 times the upper limit of normal
  - c. Excessive alcohol intake
  - d. Suboptimally treated thyroid disease
  - e. Medullary carcinoma of the thyroid or MEN-2 (in participant or a family history)
  - f. Hypertriglyceridemia (>400 mg/dl despite treatment)
9. Conditions or behaviors likely to affect the conduct of the RISE Study
  - a. Unable or unwilling to give informed consent
  - b. Unable to adequately communicate with clinic staff
  - c. Another household member is a participant or staff member in RISE
  - d. Current, recent or anticipated participation in another intervention research project that would interfere with any of the interventions/outcomes in RISE
  - e. Weight loss of >5% in past three months for any reason other than post-partum weight loss. Participants taking weight loss drugs or using preparations taken for intended weight loss are excluded.
  - f. Likely to move away from participating clinics in next two years
  - g. Women of childbearing potential who are unwilling to use adequate contraception
  - h. Current (or anticipated) pregnancy and lactation.
  - i. Major psychiatric disorder that, in the opinion of clinic staff, would impede the conduct of RISE
10. Additional conditions may serve as criteria for exclusion at the discretion of the local site.

Further details pertaining to exclusion criteria are specified in the Manual of Procedures.

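### At nominal visit dates, the anemia discontinuation clause in Protocol 7.4 cannot operate for anemia first found at a scheduled test

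*Protocol*

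**What the plan says.** **Rule.** Protocol 7.4 (Anemia) defines anemia as a hematocrit below 30%, a hemoglobin below 10 g/dl, or a fall from entry of 4% in hematocrit or 2 g/dl in hemoglobin. It then states: "If anemia persists for more than six months despite appropriate therapy, consideration will be given to discontinuing study medication".

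**Entry.** Section 3.6 excludes "Anemia (hemoglobin <11 g/dl in women, <12 g/dl in men").

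**Testing.** The Table 2 row "Hemoglobin or Hematocrit" is marked at baseline, month 6 and month 12. The text of 6.1.1 and 6.3.3 gives only screening and six months.

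**End of drug.** Section 3.4.7 says that once the clamp and OGTT are complete "after 12 months of the intervention, study medications will be stopped".

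**Start of metformin.** It differs by arm. The metformin arm starts at once: "participants will be titrated over four weeks from a starting dose of 500 mg once daily". In the liraglutide arm, "Once the maximal dose of liraglutide has been reached and is tolerated, metformin will be initiated and titrated as described above". In the glargine arm, "Following 3-months of insulin treatment, insulin glargine will be discontinued and metformin will be commenced and titrated as above".

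**Other routes to detection.** Under 7.4, participants who "experience any side effects of medications or study procedures will be instructed to call the clinical site". Section 8.3 counts significantly abnormal laboratory results between visits as adverse events.

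**A comparable rule.** The renal item in 7.4 acts on the month-6 result. Metformin stops below an eGFR of 30, and the RISE Safety Committee reviews values from 30 to below 45.

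**The concern.** The clause sets a waiting period of more than six months. From the first scheduled test that could start it, only six months of treatment remain. A site that follows the schedule and the clause to the letter reaches the point of considering discontinuation when there is no drug left to stop. No hemoglobin is scheduled between months 6 and 12, so the plan provides no test that would show, while drug remains, whether the anemia has resolved.

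At stake are individual safety decisions for a small number of participants. Section 7.3 describes megaloblastic anemia with metformin as rare, and the documents give no rate for anemia as 7.4 defines it.

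**Working it through.** The plan states no figure to reproduce, so this is a check of dates. I take 3 months as 13 weeks.

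**Inputs.** First scheduled on-study test: week 26 (Table 2; 6.1.1; 6.3.3). Persistence required: more than 26 weeks despite therapy (7.4). Drug stop: week 52 (3.4.7). Visit windows: 1 to 2 weeks either side, encouraged (6.4). Earliest metformin start: week 0 in the metformin arm; week 2 in the liraglutide arm, after one week at 0.6 mg and one at 1.2 mg (3.4.4); week 13 in the glargine arm (3.4.5).

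**1. Nominal dates.** 26 + more than 26 = later than week 52. Drug remaining: 0 weeks. A case first found at month 12 also leaves 0 weeks.

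**2. Visit windows pulled in opposite directions.**
- Test 1 week early, stop 1 week late: 25 + 26 = 51; 53 − 51 = 2 weeks.
- Test 2 weeks early, stop 2 weeks late: 24 + 26 = 50; 54 − 50 = 4 weeks.
- Test 2 weeks late, stop 2 weeks early: 50 − 28 = 22 weeks between them, short of 26.

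The most that can remain is therefore about 4 weeks. Using it would need an unscheduled test near week 50 to document persistence.

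**3. Unscheduled detection.** For the clause to operate before week 52, anemia must be found before 52 − 26 = week 26. Metformin exposure by then, and planned in total:

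| Arm | Metformin starts | Exposure by week 26 | Planned total |
|---|---|---|---|
| Metformin | week 0 | 26 weeks | 52 weeks |
| Liraglutide + metformin | week 2 at earliest | at most 24 weeks | at most 50 weeks |
| Glargine, then metformin | week 13 | 13 weeks | 39 weeks |

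The route exists in every arm. It is narrowest in the glargine arm, where 4 of the 13 weeks are titration.

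**4. What a month-9 repeat would allow.** 52 − 39 = 13 weeks before the planned stop, less review time. As a share of planned metformin time this is 13/52 = 25%, 13/50 = 26% and 13/39 = 33% in the three arms. These are best cases per flagged participant, and they come from shortening the waiting period from more than six months to three. They do not apply to placebo, where there is no metformin to spare.

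**5. Extra tests.** For each 1% of participants flagged: 255 × 0.01 = 2.55 among those recruited, or 224 × 0.01 = 2.24 among the planned completers.

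**The case against.** The strongest reply is that the clause is redundant, not breached. It tolerates six months of drug during treated anemia. For a month-6 case, the planned month-12 stop takes the participant off drug at about that same limit. This stands. A reader might infer that the protocol keeps anemic participants on drug longer than its own rule permits; at nominal dates it does not, and the only excess is the window-edge case of at most 4 weeks.

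A reader might also infer that the clause can never be triggered. The documents do not support that either, because a participant's call or an outside laboratory result before month 6 can start the waiting period in time. Nor does 7.4 forbid an earlier stop: the clause does not say that discontinuation may be considered only then. Abnormal laboratory results are adverse events (8.3) that the Safety Monitoring Committee reviews (8.4).

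It can further be said that a long observation period is a defensible choice, since the definition includes falls from entry that may leave the absolute value normal. That is fair. Nothing in the documents shows that three months is the right period, so the 13 weeks measure an opportunity for review and not a harm in the present plan. Section 5.1 also refers problems unrelated to diabetes to primary care, where treatment and repeat counts may occur. The protocol does not, however, schedule or require such a repeat.

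Counting persistence from onset instead of detection does not rescue the clause. It requires persistence despite therapy, and therapy follows detection.

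**Conclusion.** The point holds in a limited form and is worth considering at low priority. At nominal dates, the discontinuation step has 0 weeks in which to operate for anemia first found at a scheduled test. With visit windows it has at most about 4 weeks, and then only with an unscheduled test. What is wrong is a written safeguard with no practical effect for scheduled cases, and no scheduled retest between months 6 and 12.

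This rests on reading the Table 2 marks as baseline, month 6 and month 12, and on counting persistence from detection. The number of participants affected cannot be estimated from the documents. A reader might look for a consequence for the trial's conclusions, but the primary and secondary outcomes, the sample size and the analysis in the SAP do not use this clause. The missing month-12 test in 6.1.1 and 6.3.3 is a clerical mismatch with Table 2.

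**What to change.** Keep the anemia definition in 7.4 and replace the persistence sentence with wording such as:

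> If anemia is found at month 6, evaluate it and treat or refer to primary care in line with section 5.1. Repeat hemoglobin or hematocrit at the month-9 visit. If anemia is still present, the RISE Safety Committee reviews, masked, whether to continue metformin or its placebo. Anemia found at an unscheduled test follows the same steps, with the repeat at the next quarterly visit.

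This follows the pattern of the renal item: a review, not an automatic stop. Masked review matches how the Safety Monitoring Committee already works (7.2.2, 8.4).

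As an accompanying correction, align 6.1.1 and 6.3.3 with Table 2 (baseline, month 6, month 12), and note the month-9 repeat for those flagged at month 6.

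The cost is wording in three sections and one local blood test at an existing visit, where blood is already drawn for HbA1c: about 2.6 tests per 1% flagged among 255. Placebo participants would be flagged and retested too, without any metformin to spare. The Committee gains a few cases, and a three-month repeat may lead to a few earlier stops than a longer observation period would.
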